CT = computed tomography; C-SSRS = Columbia-Suicide Severity Rating Scale; ECG = electrocardiogram; ECG = electrocardiogram; ERP = event-related potential; FSH = follicle-stimulating hormone; fT3 = free tri-iodothyronine; fT4 = free thyroxine; GDS = Geriatric Depression Scale; HR = heart rate; IMP = investigational medicinal product;

MOCA = Montreal Cognitive Assessment; MRI = magnetic resonance imaging; NMSS = Non-Motor Symptom Scale; PK = pharmacokinetic; SC = subcutaneous; TSH = thyroid-stimulating hormone.

- a If 28 days is not sufficient to complete the Screening period, the possibility of an extension can be discussed with the Medical Monitor.
- b Only weight collected at Baseline/Day 1 (Visit 2b), Week 12 (Visit 5), Week 26 (Visit 8), and Safety follow-up (Visit 9).
- c Urine pregnancy test will be performed for females with child-bearing potential at screening.
- d Blood collection for FSH levels (to confirm post-menopausal state in females), serology, genotyping, fT3, fT4, and TSH.
- e 'C-SSRS Baseline/Screening' version will be administered at Screening and 'C-SSRS Since Last Visit' version will be administered at all post-Screening visits.
- f Dispensing of kits containing study drug will occur every 2 weeks; drug returns will be recorded and compliance calculated. Larger provision of study drug is permitted to accommodate personal need, e.g., vacation; site should check in with subject/caregiver via phone approximately every 2 weeks in cases of larger dispensing. IMP administration by the caregiver will be assessed at Visits 2b through 8, inclusive.
- g First SC injection of IMP will be performed at site under supervision; subject should withhold IMP dose on the day of subsequent clinic visits (IMP administration will be done on site under supervision of site staff; training of proper injection techniques for subject/caregiver will be performed as needed); subjects will remain at site for 2 hours ± 15 minutes for safety observation follow up after first SC injection of IMP.
- h Physical and neurological exam to be done post-dose at all visits where subjects are dosed.
- i MRI (or CT) scan if not done since the initial diagnosis of PD.
- j 12-lead ECGs will be performed pre-dose and 30 (± 15) minutes post-dose on Day 1(Visit 2b) and 30 (± 15) minutes post-dose at all other visits. All ECG assessments will be performed in triplicate.

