### 4.2 Inclusion Criteria

- 1. Age 40 to 85 years, inclusive at the time of signing the informed consent.
- 2. Subjects with a confirmed diagnosis of PDD (Emre, 2007), or DLB (McKeith, 2017), preferably documented by subject medical records; caregiver reports with examples are acceptable.
- 3. MOCA score 11 to 23 inclusive at the Screening visit.
- 4. Body mass index (BMI) of between  $\geq 16$  and  $\leq 35$  kg/m^2 for females and between  $\geq 18$  and  $\leq 35$  kg/m^2 for males at Screening.
- 5. Female subjects of child-bearing potential must not be pregnant (i.e., a negative urine pregnancy result is required prior to randomization) and must not be breastfeeding.
- 6. Male and female subjects of child-bearing potential and their partners must agree to use a double-barrier method of contraception during the study, including the follow-up period, unless the partner is not of childbearing potential. Female subjects of non-childbearing potential (i.e., permanently sterilized, postmenopausal) are eligible for participation.
- 7. Reliable and capable support person/caregiver, who is willing to accept responsibility for supervising the treatment or, if required, administering study drug, and assessing the condition of the subject throughout the study in accordance with all protocol requirements. The support person/caregiver must see the subject at least once-daily for dose administration and/or observation.
- 8. Subject capable of giving signed informed consent, which includes compliance with the requirements and restrictions listed in the ICF and in this protocol. If the subject is incapable of giving informed consent in the judgment of the investigator then consent may be provided by a legally acceptable representative.
- 9. Written informed consent from a) subject or legally acceptable representative and b) caregiver/support person has been obtained prior to any study-related procedures, including prior to initiating screening procedures to evaluate eligibility for the study.

- 10. Written documentation has been obtained in accordance with the relevant country and local privacy requirements, where applicable (e.g., Written Authorization for Use and Release of Health and Research Study Information).
- 11. Subjects and caregivers/support persons are able, as assessed by the investigator, and willing to follow study instructions and likely to complete all required study visits.

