#### 4.3 Exclusion Criteria

- 1. Subjects at modified Hoehn-Yahr stage 5.
- 2. History of significant neurologic disease, other than PDD or DLB that may affect cognition, or concurrent neurological disease diagnosed at the time of onset of dementia.
- 3. Subject has had neurosurgical procedure for treatment of PD (such as deep brain stimulation implant), or if such procedure is anticipated or planned during the study period.
- 4. History of brain magnetic resonance imaging (MRI) scan indicative of any other significant abnormality, which would explain a dementing process other than PDD or DLB. Note: a new MRI scan is required if not done at or since the initial diagnosis of PD; a repeat MRI scan is required if there have been intervening changes to the subject's clinical presentation in the past 12 months. CT scan is acceptable for subjects fitted with a non-MRI-safe cardiac pacemaker, or other relevant medical reason, with Medical Monitor approval.
- 5. History of unexplained loss of consciousness, or epileptic fits (unless febrile).
- 6. Inability to hear or differentiate the 2 different tones necessary for auditory ERP P300 assessment, using the centrally provided ERP equipment; subjects who wear a hearing aid must remove their hearing aid during the screening auditory test and during ERP P300 recordings.
- 7. Diagnosis with current symptoms of severe major depressive disorder (GDS score [15-item scale] > 7 at Screening). In discussion with the Medical Monitor, subjects with a GDS score between 8 and 10 inclusive can be considered for study participation if the increased score is driven by specific domains related to the pandemic and its restrictions, rather than by major depression.
- 8. Significant suicide risk as defined by suicidal ideation based on the C-SSRS within the last 12 months, at Screening and on Day 1 (i.e., a 'yes' response to Question 4 or 5, or any specific behaviors).
- 9. Significant psychosis (according to the Diagnostic and Statistical Manual of Mental Disorders, [5th edition; DSM-5; American Psychiatric Association, 2013]) interfering with

- the ability of the subject to complete study procedures in the judgment of the investigator, for reasons such as requirement to reduce previously stable dopaminergic therapy.
- 10. Moderate or severe substance abuse disorder (according to DSM-5; American Psychiatric Association, 2013).

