#### 5.4.2 Randomization Numbers

Prior to dosing on Day 1, subjects will be assigned a randomization number generated by an IRT system; the randomization numbers will subsequently be incorporated into the Electronic Data Capture (EDC) system.

Once a randomization number has been allocated to 1 subject, it may not be assigned to another subject.

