# 6.4.3 Clinical Laboratory Assessments

The following laboratory variables will be determined as outlined in Table 4 below:

Table 4 Clinical Laboratory Assessments

Test	Parameters				
Hematology	CBC	Leukocytes (WBC)			
	Hb1Ac	Differential WBC			
	Hemoglobin	Platelets			
	Hematocrit				
	Erythrocytes (RBC)	Erythrocytes (RBC)			
Biochemistry	Sodium	GGT			
	Potassium	CPK			
	Magnesium	Total bilirubin			
	FSH (post-menopausal females only) a	Total protein			
	Calcium	Albumin			
	Chloride	Total Cholesterol			
	Glucose	Low-density lipoprotein			
	Creatinine	High-density lipoprotein			
	ALP	Triglycerides			
	AST	TSH, fT3 and fT4 a			
	ALT				

Coagulation	INR PT	aPTT
Serology	HBsAg a HCV a	HIV type 1 or type 2 a
Urinalysis	pH glucose ketones specific gravity HCG (females of child-bearing potential only)	nitrite protein bilirubin blood

AST = aminotransferase; ALP = alkaline phosphatase; ALT = alanine transaminase; CBC = complete blood count; CPK = creatine phosphokinase; FSH = follicle-stimulating hormone; GGT = gamma-glutamyl transferase; Hb1Ac = glycated hemoglobin; HBsAg = hepatitis B surface antigen; HCG = human chorionic gonadotropin; HIV = human immunodeficiency virus; INR = international normalized ratio; PT = prothrombin time; aPTT = activated partial thromboplastin time; RBC = red blood cells; fT3 = free tri-iodothyronine; fT4 = free thyroxine; TSH = thyroid-stimulating hormone; WBC = white blood cells.

Any value outside the normal range will be flagged for clinical interpretation by the investigator or designee at the site. In this study, ALT or AST > 2 times the upper limit of normal, or Child-Pugh class B and C (i.e., including total bilirubin, albumin, and INR values), will be exclusionary. For transaminase liver enzymes, a repeat laboratory assessment may be performed if outside of the normal range. If the transaminases remain elevated the investigator should consider stopping study medication and withdrawing the subject as described in Section 5.8.

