A medical alert for potential Hy's laws cases (possible drug-induced liver injury) will be issued based on laboratory values and supported by Medical Monitor interpretation. Investigators, the Sponsor, Medical Monitor, and MMS (the Sponsor's designated vendor for Drug Safety and Pharmacovigilance) will immediately be notified when the above criteria have been met through a central laboratory alert. The AE eCRF should be completed within 3 business days. Every effort to determine the cause of the liver enzyme abnormalities must be made, and close monitoring should be initiated in conjunction with the Medical Monitor and in accordance with the FDA Guidance for Industry, Drug-Induced Liver Injury: Premarketing Clinical Evaluation, July 2009.

Criteria for potential Hy's law cases are as follows:

- ALT or AST  $\geq$  3 × ULN AND
- Total bilirubin  $\geq 2 \times ULN \text{ AND}$
- Alkaline phosphatase < 2 × ULN

Typically, all 3 analytes will be obtained from the same sample, but they may come from multiple samples taken within a 24-hour period. This requirement applies from the time the subject signs the ICF for the study until 4 weeks after the final protocol-defined study visit or the last known dose of study treatment (if the final visit does not occur).

<sup>a Measured only at Screening for eligibility; not included in subsequent safety labs.

Any clinically significant abnormalities from Screening labs must be discussed with the Medical Monitor to confirm eligibility of the subject. Additional testing during the study may be done if medically indicated. If a clinically significant abnormality is found in the samples taken after dosing, during the study, and/or at the safety follow-up visit, it should be recorded as an AE and the subject will be followed until the test(s) has (have) normalized or stabilized.

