#### 7.1 Schedule and Order of Assessments

The study will consist of up to 28 days of Screening (Day -32 through Day -4), a Pre-baseline visit (Visit 2a, Day -10 to Day -3), Baseline (Visit 2b, Day 1, randomization), followed by 26 weeks of double-blind treatment, and a 4-week safety follow-up. Note: if 28 days is not sufficient to complete the screening period, the possibility of an extension can be discussed with the Medical Monitor.

All assessments to be performed during the study are detailed by visit/timepoint in Table 1. For clinical outcome assessments evaluating subject's cognitive condition, the general order should be followed:

- (1)
- (2) ADAS-Cog13
- (3)
- (4) ERP P300 assessments

All cognitive assessments including MMSE, ADAS-Cog13, and shall occur at clinic visits in the morning, in the specified order when applicable.

ADAS-Cog13 assessments will be performed pre-dose at Baseline/Day 1 (Visit 2b), and post-dose at approximately 1 hour (± 30 minutes) at Week 2 (Visit 3), Week 12 (Visit 5), Week 20 (Visit 7), and Week 26 (Visit 8).

The order of assessments and timing for all other endpoints are flexible.

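### The pregnancy test that qualifies a subject is scheduled at Screening only and has no maximum age; a Day 1 urine HCG appears to be scheduled, but nothing requires it to be read before randomization or first dose

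*Protocol*

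**What the plan says.** **Eligibility.** Inclusion 5 (Protocol Section 4.2, repeated in the synopsis) excludes pregnant subjects and adds that "a negative urine pregnancy result is required prior to randomization". It gives no visit and no limit on the age of the result.

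**Schedule.** In Table 1 the Pregnancy Test row is marked at Screening and nowhere else. Footnote c reads "Urine pregnancy test will be performed for females with child-bearing potential at screening". SAP Appendix 2 carries the same row and footnote.

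**Timing.** Section 7.1 places Screening between Day -32 and Day -4. Table 1 footnote a leaves that open-ended: "If 28 days is not sufficient to complete the Screening period, the possibility of an extension can be discussed with the Medical Monitor". Randomization and the first injection both take place at Visit 2b, and Section 5.4.2 fixes their order: "Prior to dosing on Day 1, subjects will be assigned a randomization number generated by an IRT system".

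**Laboratory panel.** Table 4 (Section 6.4.3) lists HCG under urinalysis for female subjects of child-bearing potential. It does not carry footnote a, "Measured only at Screening for eligibility; not included in subsequent safety labs", which is attached to FSH, the thyroid tests and serology. The Table 1 footnote on safety labs includes urinalysis, and the Safety Labs row is marked at Screening, at Visit 2b and at every later visit. SAP Table 3 lists HCG in the same way.

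**The concern.** A negative pregnancy test describes the subject only up to the time it was taken. If the plan accepts a Screening result on Day 1, a subject who conceives in the interval meets the written test requirement and can be randomized and injected with an investigational drug. She may not know that she is pregnant, so the general bar on pregnant subjects does not necessarily catch her.

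The protocol does name Day 1 where it wants an eligibility item assessed again: exclusion 8 defines suicide risk "based on the C-SSRS within the last 12 months, at Screening and on Day 1". Inclusion 5 has no comparable wording. What is at stake is the safety of a small number of subjects. The treatment comparison is not affected.

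**Working it through.** **1. The plan's own figure.** Section 7.1 gives Screening as up to 28 days, Day -32 through Day -4. Elapsed days: -4 - (-32) = 28, which reproduces it (29 if both end days are counted).

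**2. Day-count convention.** Section 3 places Visit 2b no more than 10 days after the Pre-baseline visit, whose earliest day is Day -10. Day -10 to Day 1 is 10 days only if there is no Day 0: 1 - (-10) - 1 = 10. I therefore count without a Day 0.

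**3. Age of a Screening result at first dose.** For a test on Day d and a first dose on Day 1, age = 1 - d - 1.

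| Test day | Age, no Day 0 | Age, with a Day 0 (1 - d) |
|---|---|---|
| Day -4 | 1 + 4 - 1 = 4 days | 5 days |
| Day -32 | 1 + 32 - 1 = 32 days | 33 days |

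**4. Extended Screening.** No cap is stated, so 32 days is not a ceiling. As an assumption only, extensions of 7, 14 or 28 days give 32 + 7 = 39, 32 + 14 = 46 or 32 + 28 = 60 days.

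**5. Does the Table 4 HCG close the gap?** The relevant texts, taken in turn:

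- Table 4 plus the Safety Labs row: read literally, urine HCG is run at Visit 2b. The result could then be 0 days old at first dose, provided it is read first.
- Timing of the sample: Table 1 fixes pre-dose timing for vital signs and for one of the Day 1 ECGs, and post-dose timing for the physical and neurological examination. The safety-labs footnote fixes none.
- Order of procedures: after setting the sequence of cognitive and ERP testing, Section 7.1 leaves the order and timing of the remaining endpoints flexible.
- Where the result comes from: Section 6.4.3 routes liver alerts through a central laboratory. This suggests, but does not prove, that safety labs are processed off site. No turnaround time is given.
- Link to eligibility: neither inclusion 5 nor footnote c refers to the Table 4 HCG.

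The Day 1 HCG may therefore be collected after the dose, or collected before it and read afterwards, without departing from any written requirement. On either reading of Table 4, the Screening result can be the only one known when the subject is randomized and dosed.

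**The case against.** The strongest reply is that the plan breaks no rule of its own. Inclusion 5 asks for a negative result before randomization and the schedule supplies one. Section 7 uses the screening evaluations to confirm eligibility, and serology is likewise tested once, at Screening. The comparison with exclusion 8 is an argument from silence, because that criterion concerns suicidality over a look-back period. Safeguards also surround the gap:

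- inclusion 5 itself bars pregnant subjects, and eligibility is marked for review at Visits 2a and 2b;
- double-barrier contraception is required (inclusion 6 and Section 7.3.3.2);
- FSH is measured to confirm post-menopausal status;
- Section 6.4.2 provides for withdrawal, reporting within 24 hours of learning of a pregnancy, and follow-up of the outcome.

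Much of this stands. The text is not contradictory, and the safeguards make the event unlikely. But contraception lowers a probability without verifying status, Section 6.4.2 acts only once a pregnancy is known, and the Visit 2b eligibility review is not given a current result to work from. Serology is also a weaker parallel, since pregnancy status can change at any point in the interval.

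A reader might infer that the trial does no pregnancy testing after Screening. The documents do not support that: Table 4, without the Screening-only footnote, together with the Safety Labs row points to HCG at Visit 2b and at later visits. A reader might also try to state how many doses would be given before a pregnancy was detected. That depends on a laboratory turnaround that the documents do not give, so no such number is offered here.

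**Conclusion.** The point holds as a minor gap in safety wording. The result that satisfies inclusion 5 can be 4 to 32 days old at first dose, and older after an extension. The apparent Day 1 HCG is not tied to randomization or dosing.

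The 4-to-32-day range rests on counting without a Day 0, which matches the protocol's own usage. That a Day 1 result might go unread before dosing is inferred from the absence of any timing rule, not from a statement that it will happen.

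The number of subjects exposed to this gap is unknown. The age range is 40 to 85 years, about 75 subjects were planned, and the documents do not say how many would be female and of child-bearing potential; the number could be zero. No estimate, test or sample-size figure changes. SAP Section 6 records that the study stopped early, so the practical value lies mainly in any later protocol that reuses this schedule.

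**What to change.** Run the Visit 2b urine HCG on site, before dosing, for female subjects of child-bearing potential, and make its result a condition of randomization:

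- Table 1: add a mark at Visit 2b in the Pregnancy Test row.
- Footnote c: change the timing to *at Screening and pre-dose at Visit 2b*.
- Inclusion 5, in Section 4.2 and the synopsis: state that the Visit 2b result must be negative before randomization.
- SAP Appendix 2: make the row and footnote match. No analysis is affected.

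The cost is amendment wording and one urine dipstick per eligible subject. No extra visit is needed, because urinalysis is already marked at Visit 2b. An on-site result can be available before the randomization number is assigned, and Section 5.4.2 already places that step ahead of dosing.

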# LIST OF ABBREVIATIONS AND DEFINITIONS OF TERMS

Abbreviation	Definition
AD	Alzheimer's disease
ADAS-Cog 13	Alzheimer's Disease Assessment Scale-Cognitive Subscale, 13-item
	version
AE	Adverse event
AKT	Protein kinase B
ALP	Alkaline phosphatase
ALT	Alanine aminotransferase
APP/PS1	Amyloid precursor protein/presenilin 1
aPTT	Activated partial thromboplastin time
AST	Aspartate aminotransferase
BMI	Body mass index
CBC	Complete blood count
CBD	Cannabidiol
COVID-19	Coronavirus disease – 2019
СРК	Creatine phosphokinase
CRO	Contract research organization
CYP3A4	Cytochrome P450 3A4
C max	Maximum concentration
CNS	Central nervous system
CPK	Creatine phosphokinase
C-SSRS	Columbia-suicide severity rating scale
CT	Computerized tomography
DLB	Dementia with Lewy bodies
DSM-5	Diagnostic and Statistical Manual of Mental Disorders, 5 th Edition
ECG	Electrocardiogram
eCRF	Electronic case report form
EDC	Electronic data capture
EEG	Electroencephalogram
eGFR	Estimated glomerular filtration rate
ERP	Event-related potentials

ET	Early termination
FSH	Follicle-stimulating hormone
fT3	Free tri-iodothyronine
fT4	Free thyroxine
FWER	Family-wise error rate
GBA	Glucocerebrosidase
GCP	Good Clinical Practice
GDS	Geriatric depression scale
GGT	Gamma-glutamyl transferase
GLP	Good Laboratory Practice
GST	Global Statistical Test
Hb1Ac	Glycated hemoglobin
HBsAg	Hepatitis B surface antigen
HCG	Human chorionic gonadotropin
HCV	Hepatitis C virus
HGF	Hepatic growth factor
HIV	Human immunodeficiency virus
HR	Heart rate
ICF	Informed consent form
ICH	International Council for Harmonisation
IEC	Independent ethics committee
IMP	Investigational medicinal product
INR	International normalized ratio
IRB	Institutional review board
IRT	Interactive response technology
LAR	Legally authorized representative
LBD	Lewy body dementia
LTP	Long-term potentiation
MAO-B	Monoamine oxidase B
MAPK	Mitogen-activated protein kinase
MCT	Medium-chain triglyceride
MDS-UPDRS	Movement Disorder Society – Unified Parkinson's Disease Rating Scale
MET	MET receptor tyrosine kinase
mITT	Modified intent-to-treat
MMRM	Mixed model for repeated measures
MOCA	Montreal Cognitive Assessment
MRI	Magnetic resonance imaging

NMDA	N-methyl D-aspartate	
OD	Once-daily	
OLEX	Open-label extension	
P	Phosphorylated	
PD	Parkinson's disease	
PDD	Parkinson's disease dementia	
PI3K	Phosphoinositide 3-kinase	
PK	Pharmacokinetic(s)	
PK-PD	Pharmacokinetic-pharmacodynamic	
PKC	Protein kinase C	
PLCγ	Phospholipase C-gamma	
PRN	As needed	
PT	Prothrombin time	
qEEG	Quantitative electroencephalogram	
QTcF	Corrected QT interval using Fridericia's formula	
RAC1	Ras-related C3 botulinum toxin substrate 1	
RAF	Rapidly accelerated fibrosarcoma (protein)	
RBC	Red blood cells	
SAE	Serious adverse event	
SAP	Statistical analysis plan	
SBP	Systolic blood pressure	
SC	Subcutaneous	
SOP	Standard operating procedure	
STAT3	Signal transducer and activator of transcription 3	
SUSAR	Suspected unexpected serious adverse reaction	
THC	Tetrahydrocannabinol	
TSH	Thyroid-stimulating hormone	
ULN	Upper limit of normal	
US(A)	United States (of America)	
VAS	Visual analog scale	
WBC	White blood cells	

### 1 INTRODUCTION

ATH-1017 is an experimental treatment for dementia, including Alzheimer's disease (AD) dementia, Parkinson's disease dementia (PDD), and dementia with Lewy bodies (DLB). ATH-1017 is formulated as a sterile solution for subcutaneous (SC) injection. ATH-1017 is a prodrug, which is rapidly converted to the active metabolite ATH-1001 in the plasma after SC injection. ATH-1017 was developed as a water-soluble prodrug of ATH-1001 to allow SC dosing in aqueous vehicles. The active metabolite ATH-1001 acts as an agonist of the hepatic growth factor (HGF) receptor and its tyrosine kinase, MET in the brain. The HGF/MET system presents a new therapeutic target to treat neurodegeneration and restore cognitive function in AD, PDD, and DLB.

